#### **Secondary Outcomes**

Secondary outcomes included:

- Individual complication rates, including intraperitoneal adhesions, bowel obstruction, surgical site infection, incisional hernia, and fistula formation

- Time to bowel function recovery, defined as the time to first flatus and tolerance of oral diet
- Length of intensive care unit (ICU) stay and total hospital stay
- Device-related adverse events, including infection, inflammatory reaction, or mesh-related complications
- Radiologic assessment of adhesions or obstruction using magnetic resonance imaging (MRI) at baseline, one month, and two months
- Quality of life assessment using the European Organisation for Research and Treatment of Cancer Quality of Life Questionnaire Core 30 (EORTC QLQ-C30), a validated cancer-specific instrument [20]

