### Sample Size Calculation

Based on prior literature reporting postoperative complication rates of approximately 40–45% following extensive peritonectomy, a reduction to 15–20% in the intervention group was considered clinically meaningful. The required sample size for comparing two independent proportions was estimated using the formula:

$$n = ((Z_{1-\alpha/2} + Z_{1-\beta})^2 \times [p_1(1-p_1) + p_2(1-p_2)]) / (p_1 - p_2)^2$$

where  $p_1$  represents the expected complication rate in the control group and  $p_2$  the expected rate in the intervention group,  $Z_{1-\alpha/2}$  corresponds to the two-sided significance level  $\alpha=0.05$ , and  $Z_{1-\beta}$  to the desired power (80%). Assuming  $p_1=0.40$  and  $p_2=0.20$ , the calculated minimum sample size was 26 patients per group. To account for potential dropouts and protocol deviations, 30 patients were enrolled in each arm, yielding a total sample size of 60 participants.

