### Statistical Analysis Plan

Statistical analyses were performed using SPSS version 29.0 (IBM Corp., Armonk, NY, USA). Continuous variables were assessed for normality using the Shapiro–Wilk test and are presented as mean  $\pm$  standard deviation for normally distributed data or median with interquartile range for non-normally distributed data. Between-group comparisons were conducted using the independent t-test or Mann–Whitney U test for continuous variables and the chi-square test or Fisher’s exact test for categorical variables, as appropriate. Effect estimates for the primary and key secondary binary outcomes were expressed as relative risks with 95% confidence intervals. Time-to-event outcomes, including time to bowel function recovery, were analyzed using Kaplan–Meier survival curves with log-rank testing. Multivariable logistic regression analysis was performed to adjust for potential confounders, including age, primary tumor type, peritoneal cancer index score, and use of hyperthermic intraperitoneal chemotherapy. All statistical tests were two-sided, and a p-value  $< 0.05$  was considered statistically significant. Analyses were conducted on an intention-to-treat basis.

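### MRI is read at baseline, one month and two months, but the plan names no MRI visit and states no analysis that uses the baseline reading or treats the two follow-up readings jointly

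*Combined protocol and SAP*

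**What the plan says.** Under Secondary Outcomes the combined document lists "Radiologic assessment of adhesions or obstruction using magnetic resonance imaging (MRI) at baseline, one month, and two months". That is one baseline reading and two follow-up readings per patient. The item does not say whether the reading is yes/no, a grade or a score, and it does not say which visit is compared between arms. Postoperative Care and Follow-Up adds only that imaging followed a timetable set by the protocol.

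The Statistical Analysis Plan has no MRI-specific analysis. Its general methods are:

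- **Continuous outcomes:** "Between-group comparisons were conducted using the independent t-test or Mann–Whitney U test for continuous variables".
- **Categorical outcomes:** the chi-square or Fisher's exact test.
- **Effect measure:** "Effect estimates for the primary and key secondary binary outcomes were expressed as relative risks with 95% confidence intervals".
- **Time-to-event outcomes:** Kaplan–Meier curves and the log-rank test.
- **Adjustment:** one multivariable logistic regression. Its outcome is not named, and its listed covariates are "age, primary tumor type, peritoneal cancer index score, and use of hyperthermic intraperitoneal chemotherapy".
- **Error rate:** "All statistical tests were two-sided", with significance at 0.05. No multiplicity rule is given.

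The section mentions no change from baseline, no baseline reading as a covariate, and no model for repeated readings.

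**The concern.** The Introduction says the mesh is expected to limit adhesion formation. MRI is the scheduled imaging measure of that effect. Under Randomization and Allocation its readers are to be blinded where applicable, in a trial that is otherwise open-label. So this secondary outcome deserves a clear analysis.

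Two things are at stake. The first is precision. A reading taken before treatment can explain part of the variation between patients at follow-up, and with 60 patients any such gain is useful. Here the reading is scheduled and no stated analysis draws on it. The second is the choice of visit. With two follow-up readings and none named, the visit with the more favourable result could be reported as the MRI finding, and a reader could not tell that this had happened.

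**Working it through.** **The plan's own figures.** The document gives no sample size, power or error rate for MRI, so there is no MRI figure to reproduce. Its only calculation is for the primary outcome: "the calculated minimum sample size was 26 patients per group", then "30 patients were enrolled in each arm, yielding a total sample size of 60 participants". With the stated formula and inputs (0.40 versus 0.20, two-sided 0.05, 80% power), the result is (1.960 + 0.842)² × (0.24 + 0.16) / 0.20² = 78.5, so 79 per group, not 26. That is a separate and more serious matter. The check below uses only the 30 per arm enrolled.

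**Inputs**

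- From the document: 30 per arm, 60 in total; two follow-up MRI readings; two-sided tests at 0.05.
- Assumed, because the document gives no figure: the correlation r between baseline and follow-up readings, and the correlation c between the one-month and two-month test statistics.
- Also assumed: all 60 patients have the readings.

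**1. Precision from baseline adjustment (continuous score only).** In a linear model, adjustment multiplies the variance of the arm difference by about 1 − r². The equivalent total sample size is 60 / (1 − r²). The standardised difference detectable with 80% power is (1.960 + 0.842) × √[(2/30)(1 − r²)].

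| Assumed r | 1 − r² | 60 / (1 − r²) | Detectable difference (SD) |
|---|---|---|---|
| 0 | 1.00 | 60 | 0.72 |
| 0.2 | 0.96 | 62.5 | 0.71 |
| 0.3 | 0.91 | 66 | 0.69 |
| 0.5 | 0.75 | 80 | 0.63 |
| 0.7 | 0.51 | 118 | 0.52 |

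If baseline MRI is pre-operative, cytoreduction and peritoneal stripping come between it and follow-up, and the adhesions of interest form after surgery. The first rows are therefore realistic. The table does not carry over to a yes/no reading. There, logistic adjustment does not shrink the variance of the log odds ratio by 1 − r², and it changes the effect measure.

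**2. False-positive chance if both visits are tested and either counts.** For two correlated standard normal statistics, the chance is 1 − P(|Z₁| ≤ 1.96 and |Z₂| ≤ 1.96).

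| Assumed c | Chance of at least one false positive |
|---|---|
| 0 (ceiling) | 1 − 0.95² = 9.75% |
| 0.3 | 9.5% |
| 0.5 | 9.1% |
| 0.7 | 8.3% |
| 0.8 | 7.8% |
| 0.9 | 7.0% |

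A single pre-named MRI test keeps this at 5%.

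**3. Which visit.** The primary outcome counts events within two months of surgery, and the last scheduled clinical assessment is at 60 days. The two-month MRI matches both.

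**The case against.** The strongest reply is that this is a gap in definition, not a wrong analysis. A reader might infer that the plan tests the arms separately at each visit and never uses baseline. The document says neither. It is silent on how MRI is analysed, and separate tests are only the natural reading of the methods it names. The logistic covariates are introduced as examples, so the list may not be complete, and the modelled outcome is not stated. This part of the objection stands, and the point is limited to what no stated analysis does.

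A reader might also infer that ignoring baseline wastes a large share of the information. The documents do not support that. They mention no MRI score, they list adhesions and obstruction among complication rates, and they plan relative risks for key secondary binary outcomes. A yes/no reading is therefore at least as plausible as a score. They give no correlation either, and one near zero is credible. This stands too: the size of the gain is unknown.

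A third tempting inference is that the trial has two chances of a positive MRI result. The plan has no rule that success at either visit counts, so the inflation is conditional. It is also a small part of a wider issue, since many secondary outcomes are listed with no multiplicity control.

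These replies limit the size of the point and leave the gap in place. A reader cannot assume that baseline MRI enters an unnamed model through an open-ended covariate list, and the document names no visit.

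**Conclusion.** The point holds in a limited form. The document schedules three MRI readings, names no visit for comparison, and states no analysis that uses baseline or handles the two follow-up readings together. Naming one visit and adjusting it for a reading already scheduled is a better method at almost no cost.

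If the reading is a continuous score, the benefit runs from nothing (r = 0) to the equivalent of 118 patients instead of 60 (r = 0.7), with values near the bottom plausible. These correlations are assumptions, and no comparable figure can be given for a yes/no reading. If both visits were tested at 5% and either counted, the false-positive chance would be about 7.8% to 9.5% for c from 0.8 to 0.3, against 5%. The plan does not say that this was done. The point concerns one secondary outcome and does not affect the primary analysis.

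**What to change.** Add a short MRI paragraph to the Statistical Analysis Plan that does the following:

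1. State the scale of the reading (yes/no, grade or score) and when baseline is taken. Envelopes are opened during surgery, so a pre-operative reading precedes randomisation and is a proper covariate.
2. Name the two-month reading as the single MRI comparison between arms.
3. Adjust that comparison for the baseline reading: ANCOVA for a score, ordinal regression for a grade. For a yes/no reading, use a baseline-adjusted relative risk, for example from modified Poisson regression or standardised logistic estimates. A plain logistic model would replace the planned relative risk with an odds ratio.
4. Report the one-month contrast as descriptive, with an estimate and interval.

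**Cost:** SAP wording and no new data. If baseline proves uninformative, a linear baseline term costs one degree of freedom. The document is written in the past tense, with enrolment described as complete, so the change must be dated. If MRI data have already been seen, the choice of visit and the adjustment must be labelled post hoc.

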### Sample Size Calculation

Based on prior literature reporting postoperative complication rates of approximately 40–45% following extensive peritonectomy, a reduction to 15–20% in the intervention group was considered clinically meaningful. The required sample size for comparing two independent proportions was estimated using the formula:

$$n = ((Z_{1-\alpha/2} + Z_{1-\beta})^2 \times [p_1(1-p_1) + p_2(1-p_2)]) / (p_1 - p_2)^2$$

where  $p_1$  represents the expected complication rate in the control group and  $p_2$  the expected rate in the intervention group,  $Z_{1-\alpha/2}$  corresponds to the two-sided significance level  $\alpha=0.05$ , and  $Z_{1-\beta}$  to the desired power (80%). Assuming  $p_1=0.40$  and  $p_2=0.20$ , the calculated minimum sample size was 26 patients per group. To account for potential dropouts and protocol deviations, 30 patients were enrolled in each arm, yielding a total sample size of 60 participants.

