### **Randomization and Allocation**

Eligible patients were randomized in a 1:1 ratio to either the intervention group (HPTC peritoneal reconstruction) or the control group (standard peritonectomy closure). Randomization was performed using a computer-generated block randomization sequence with variable block sizes to ensure balanced group allocation across participating centers.

Allocation concealment was achieved using sealed, opaque envelopes opened intraoperatively after completion of cytoreduction and confirmation of peritoneal defect suitability. Due to the nature of the surgical intervention, blinding of the operating surgeon was not feasible. However, outcome assessors, radiologists evaluating imaging studies, and statisticians were blinded to treatment allocation wherever applicable.

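### The printed sample size formula with its stated inputs gives 79 patients per group, not 26, so 60 patients give about 40% power rather than 80%

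*Combined protocol and SAP*

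**What the plan says.** The Sample Size Calculation section of the combined protocol and SAP starts from "postoperative complication rates of approximately 40–45% following extensive peritonectomy" and says that "a reduction to 15–20% in the intervention group was considered clinically meaningful". It then prints the standard formula for two independent proportions with unpooled variance. The control rate is set at 0.40 and the intervention rate at 0.20, the first normal quantile "corresponds to the two-sided significance level" of 0.05, and the desired power is 80%. From these the section concludes that "the calculated minimum sample size was 26 patients per group". It adds an allowance for dropouts and protocol deviations, without stating a rate, and reports that "30 patients were enrolled in each arm, yielding a total sample size of 60 participants".

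Two other sections bear on the calculation. Under Randomization and Allocation, "Eligible patients were randomized in a 1:1 ratio". Under Statistical Analysis Plan, "All statistical tests were two-sided" at the 0.05 level, and categorical outcomes are compared by chi-square or Fisher's exact test.

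**The concern.** Everything needed to reproduce the figure is printed in one paragraph, and the figure does not follow. A halving of risk from 40% to 20% is not normally detectable with 80% power in about 50 patients, so 26 per group looks wrong even before it is calculated.

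This is the plan's only justification of its size, and it supports the single primary outcome. A reader who takes the section at face value will believe that the trial had an 80% chance of detecting a halving of major complications, and could take a non-significant result as good evidence against such an effect. If true power is near 40%, a non-significant result is the more likely outcome even when the mesh works as hypothesised.

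**Working it through.** **Inputs.** From Sample Size Calculation: p1 = 0.40, p2 = 0.20, two-sided alpha 0.05 (z = 1.960), power 80% (z = 0.842). The allocation is 1:1 (Randomization and Allocation). The test is two-sided chi-square or Fisher's exact (Statistical Analysis Plan).

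**1. The plan's formula with the plan's inputs.**

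n = (z₁ + z₂)² × [p1(1 − p1) + p2(1 − p2)] / (p1 − p2)²

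- (1.960 + 0.842)² = 7.849
- 0.40 × 0.60 + 0.20 × 0.80 = 0.24 + 0.16 = 0.40
- (0.40 − 0.20)² = 0.04
- n = 7.849 × 0.40 / 0.04 = 78.49, so **79 per group**, 158 in total before any allowance

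The stated 26 is not reproduced.

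**2. Could another reading give 26?** Other methods at 40% against 20%, two-sided, need more patients: 82 with pooled variance, 81 with the arcsine method and 91 with a continuity correction. Applying the plan's formula across its stated ranges, at 80% power:

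| Control vs intervention | Two-sided 0.05 | One-sided 0.05 |
|---|---|---|
| 40% vs 20% | 78.5 → 79 | 61.8 → 62 |
| 40% vs 15% | 46.2 → 47 | 36.4 → 37 |
| 45% vs 20% | 51.2 → 52 | 40.3 → 41 |
| 45% vs 15% | 32.7 → 33 | 25.8 → 26 |

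Only 45% against 15% at one-sided 0.05 gives 26. That may be where the figure came from, but the documents show no such calculation, and it contradicts both the stated rates and the two-sided alpha.

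**3. Power at the actual size.** By the plan's formula, power = Φ(|p1 − p2| / √([p1(1 − p1) + p2(1 − p2)]/n) − 1.960). For 40% against 20% with n = 30 this is Φ(0.20/√(0.40/30) − 1.960) = Φ(−0.228) = 0.41. The exact values below come from full enumeration of the two binomial distributions.

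| Evaluable per arm | True rates | Plan's formula | Exact, uncorrected chi-square | Exact, Fisher |
|---|---|---|---|---|
| 30 | 40% vs 20% | 41% | 39% | 30% |
| 26 | 40% vs 20% | 36% | 37% | 25% |
| 30 | 45% vs 15% | 77% | 74% | 64% |
| 30 | 40% vs 10% | 82% | 80% | 71% |
| 26 | 40% vs 10% | 76% | 75% | 62% |

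With 30 per arm, 80% power is not reached anywhere in the plan's ranges. It needs roughly 40% against 10%, and then only with all patients evaluable and the chi-square test. The 10% rate lies outside the plan's 15–20% and is shown only for scale.

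**4. If the planned effect is observed exactly.** With 12/30 against 6/30:

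- Chi-square = 2.857, p = 0.091; Fisher p = 0.16.
- RR = 0.20/0.40 = 0.50.
- SE of log RR = √(1/6 − 1/30 + 1/12 − 1/30) = 0.428.
- 95% CI = 0.50 × exp(±1.96 × 0.428) = 0.22 to 1.16.

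**5. Dropout allowance.** No rate is stated. Scaling by the plan's own step from 26 to 30 gives 79 × 30/26 = 91.2, so about 92 per arm. This is an assumption, not a figure from the documents.

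**The case against.** The arithmetic itself has no good defence: the formula, inputs and result are all legible, and nothing elsewhere in the document corrects them. The fair objections concern what follows from it.

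- **Desired power is not achieved power.** The 80% enters as a target for the formula, and the plan never separately states what 60 patients achieve. This stands as a matter of wording. The accurate criticism is that the size does not deliver the power it was calculated for. A reader would still infer 80%.
- **Enrolment is described in the past tense.** If it is complete, a larger trial is no longer a matter of editing. This stands, and it is why the fix offers a route that keeps 60 patients.
- **Relative risks with 95% confidence intervals are already planned** for the primary outcome. This also stands. An interval will show the imprecision, but it neither corrects the sample size statement nor says how a non-significant result will be read.
- **About 40% is itself conditional.** It assumes all 60 patients are evaluable and an uncorrected chi-square test. With Fisher's exact test, or with 26 evaluable per arm, power is lower. This makes the concern larger, and any replacement text should name the test and the evaluable number.

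**Conclusion.** The concern holds and must be fixed. The stated formula and inputs give 79 per group; the plan reports 26, about one third of that. This result uses only figures printed in the plan.

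The power at 30 per arm for the assumed 40% against 20% is about 40% (41% by formula, 39% exact chi-square), provided all patients are evaluable. It is 30% with Fisher's exact test, and 25–37% across the three methods if only 26 per arm are evaluable. Even the most favourable pair in the plan's ranges stays below 80%. The trial is therefore more likely than not to give a non-significant primary result if the assumed effect is real.

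**What to change.** Correct the calculated minimum to 79 per group, and state the dropout rate used to inflate it. With the same proportional allowance as the plan's step from 26 to 30, the enrolment figure would be about 92 per arm.

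Then take one of two routes:

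1. **Enlarge the trial to the corrected figure.** At about 92 per arm this means 184 patients instead of 60, which is a substantial cost and may not be possible if enrolment has closed.
2. **Keep 60 patients and restate the power.** Remove the implication that this size gives 80% power. Suggested text: *With 30 evaluable patients per arm and a two-sided 0.05 test, power to detect 40% against 20% is about 40% with the uncorrected chi-square test and about 30% with Fisher's exact test. Power of about 80% is reached only for a difference of about 40% against 10%, with the chi-square test. Power is lower if fewer patients are evaluable.* This costs one recalculated figure and some wording, with no added patients. The stated power becomes much less favourable.

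Under the second route, keep the planned relative risk with 95% confidence interval as the main presentation of the primary result, add the risk difference with its interval, and state in advance that p > 0.05 will not be interpreted as evidence of no effect.

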### Statistical Analysis Plan

Statistical analyses were performed using SPSS version 29.0 (IBM Corp., Armonk, NY, USA). Continuous variables were assessed for normality using the Shapiro–Wilk test and are presented as mean  $\pm$  standard deviation for normally distributed data or median with interquartile range for non-normally distributed data. Between-group comparisons were conducted using the independent t-test or Mann–Whitney U test for continuous variables and the chi-square test or Fisher’s exact test for categorical variables, as appropriate. Effect estimates for the primary and key secondary binary outcomes were expressed as relative risks with 95% confidence intervals. Time-to-event outcomes, including time to bowel function recovery, were analyzed using Kaplan–Meier survival curves with log-rank testing. Multivariable logistic regression analysis was performed to adjust for potential confounders, including age, primary tumor type, peritoneal cancer index score, and use of hyperthermic intraperitoneal chemotherapy. All statistical tests were two-sided, and a p-value  $< 0.05$  was considered statistically significant. Analyses were conducted on an intention-to-treat basis.

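### Hospital stay, ICU stay, quality of life and bowel recovery have no planned between-arm estimate or interval, and a normality test on the trial's own data sets how the continuous outcomes are reported

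*Combined protocol and SAP*

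**What the plan says.** Two rules in the Statistical Analysis Plan section meet here.

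- **Choice of summary and test.** "Continuous variables were assessed for normality using the Shapiro–Wilk test", and the result decides between mean with SD and "median with interquartile range for non-normally distributed data". The next sentence reads "Between-group comparisons were conducted using the independent t-test or Mann–Whitney U test for continuous variables" and leaves the choice to whichever is suitable. No criterion other than normality is given. The plan does not say whether normality is checked by arm, on the pooled data or on residuals.
- **Effect estimates.** "Effect estimates for the primary and key secondary binary outcomes were expressed as relative risks with 95% confidence intervals". No corresponding sentence exists for continuous outcomes. For the rest, "Time-to-event outcomes, including time to bowel function recovery, were analyzed using Kaplan–Meier survival curves with log-rank testing", with no hazard ratio or other contrast. The only regression model named is logistic.

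The Secondary Outcomes section has six bullets. Among them are "Length of intensive care unit (ICU) stay and total hospital stay", time to bowel function recovery, and "Quality of life assessment using the European Organisation for Research and Treatment of Cancer Quality of Life Questionnaire Core 30". The questionnaire scales to be analysed, their scoring and their time point are not stated.

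**The concern.** A secondary outcome reported as two arm summaries and a p-value does not tell the reader how large the effect is or how precisely it was measured. With 30 patients per arm, non-significant results are likely even when effects are real. Without an interval, no effect cannot be told from too little information.

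The normality test adds a second problem. The form of the report then depends on a preliminary test result and not on the question asked. Questionnaire scores take a limited set of values, so a scale with few levels will tend to fail the test and be reported by medians, while a finer scale may pass. On a coarse scale the median can stay at the same level in both arms although the means differ.

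**Working it through.** The plan gives no figure on this point. Its one calculated figure, the sample size, concerns the primary outcome; only the 30 per arm (Sample Size Calculation) is used below.

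**1. Each outcome traced through the plan**

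| Outcome | Arm summary | Test | Between-arm estimate with CI |
|---|---|---|---|
| Binary, primary and key secondary | counts | chi-square or Fisher | relative risk, 95% CI |
| Hospital stay, ICU stay | mean/SD or median/IQR, by Shapiro–Wilk | t-test or Mann–Whitney | none |
| QLQ-C30 | as for stay | as for stay | none |
| Bowel recovery | Kaplan–Meier curve | log-rank | none |

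Three of the six secondary bullets (stay, quality of life, bowel recovery) have no planned estimate. Two of the six (stay, quality of life) are subject to the normality test. Treating stay as time-to-event would not help, since that route also ends in a log-rank p-value.

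**2. What an interval would show**

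Half-width of the 95% CI for a difference in means, 30 per arm: t(0.975; 58) × SD × √(2/30) = 2.002 × 0.258 × SD ≈ 0.517 × SD. The documents give no SD; assumed 20, 25 and 30 give ±10.3, ±12.9 and ±15.5 points. Power for a 10-point difference is about 49%, 34% and 25%. A non-significant p-value would therefore say little by itself.

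**3. Quality of life**

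Assumptions: 0–100 score, normal with control mean 60 and SD 20 or 25, 10-point shift, clipped to 0–100 and rounded to 4, 7 or 13 levels; 30 per arm, 1,500 trials per setting. The mean difference after clipping and rounding is 9.0–9.7 points.

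| Levels | Shapiro–Wilk rejects in at least one arm | Arm medians equal | Medians equal among trials significant by Mann–Whitney |
|---|---|---|---|
| 4 | 100% | 92–97% | 78–93% |
| 7 | 97–99% | 39–47% | 8–17% |
| 13 | 36–54% | 12% | under 1% |

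The results depend on where the mean sits. Across all runs made with a shift of about 10 points, medians are equal in 41–97% of trials with 4 levels, 24–47% with 7, and 8–13% with 13 to 16. Rejection with 13 to 16 levels ranges over 14–95%.

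**4. Stay**

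Assumed log-normal, rounded to whole days.

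- Hospital stay, medians 12 and 10 days, log-SD 0.3, 0.5 and 0.7: Shapiro–Wilk rejects in 42%, 74% and 93% of control arms. The two arms get opposite verdicts in 50%, 38% and 14% of trials, a case for which the plan has no rule.
- Hospital stay, median 14 days, ratio 1.0 or 0.75: the rule selects Mann–Whitney in 64–100% of trials, and the two tests disagree at 0.05 in 2–14%. Type I error of the two-stage rule is 4.0–5.5% over two independent runs.
- ICU stay, medians 2.5 and 2 days: Shapiro–Wilk rejects in 99–100% of control arms, and the arm medians are equal in 37–43% of trials. The Hodges–Lehmann estimate is exactly 0 in 49–58%, so it would be a poor remedy for this outcome.

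**The case against.** The strongest reply is that the normality test does little harm. Type I error is near nominal, the two tests seldom disagree, and for skewed stay data the rule mostly picks Mann–Whitney anyway. Where normality is accepted, arm means, SDs and numbers let a reader work out the difference and its interval. All of this stands. It narrows the point to estimation and consistency, and makes the missing estimate the more important part. It does not answer the median branch or the Kaplan–Meier route, where the planned output gives no between-arm interval.

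Four stronger readings are tempting and are not supported.

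- *The normality test causes the missing estimate.* It does not. Estimates are confined to binary outcomes whichever way the test falls, so deleting the test alone would add nothing.
- *The plan states that Shapiro–Wilk picks the hypothesis test.* It ties Shapiro–Wilk explicitly only to presentation. The link to the test is a reasonable inference, since no other criterion appears.
- *Half of the secondary outcomes reduce to two medians and a p-value.* Bowel recovery is outside the normality rule. Only two of six bullets fall under it, and they get medians only when normality is rejected.
- *QLQ-C30 medians will nearly always coincide.* The high figures belong to an assumed 4-level scale. The documents name no scale and give no level count, mean or SD, and with 13 to 16 levels medians coincide in only 8–13% of trials.

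**Conclusion.** The point holds in limited form. That hospital stay, ICU stay, QLQ-C30 and bowel recovery have no planned between-arm estimate or interval follows from the text and needs no assumption. That the normality test makes the report data-dependent is explicit for the summary and implied for the test.

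The size of the coinciding-medians problem rests on assumed score distributions: substantial for 4 to 7 levels, small for 13 or more. The stay figures rest on assumed log-normal distributions. The primary analysis is not affected and no error rate is inflated. This is a change that should be made to the secondary analyses, not a threat to the trial's main conclusion.

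**What to change.** Drop the normality test as a decision rule and fix one analysis per outcome in advance:

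- **QLQ-C30:** for every scale reported, the difference in means with 95% CI. The scales, the time point and the handling of any baseline score must be named too, since the plan states none of them.
- **Hospital stay:** Mann–Whitney, with the Hodges–Lehmann difference in days and 95% CI.
- **ICU stay in whole days:** Mann–Whitney, with the difference in mean days and a bootstrap 95% CI, because medians are often tied and the Hodges–Lehmann estimate is often exactly zero.
- **Bowel recovery:** keep the log-rank test and add the difference in restricted mean time up to a prespecified day, with 95% CI.

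Medians and IQRs may still be shown as description. The cost is a few sentences and a few more analyses, with no new data, and a slight loss of efficiency from Mann–Whitney if hospital stay proves close to normal. The plan is written in the past tense; if the analyses have already been run, the estimates can be added from the collected data and labelled as not prespecified.

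### For uncommon individual complications at 30 per arm, Fisher's exact test is valid but conservative; naming Boschloo's test (or mid-P) with a stated trigger is a cheap improvement

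*Combined protocol and SAP*

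**What the plan says.** All places are in the combined protocol and SAP.

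- **Test.** The Statistical Analysis Plan section allows chi-square or Fisher's "exact test for categorical variables, as appropriate". It gives no threshold for choosing between them, and mentions no continuity correction, mid-P value or unconditional exact test.
- **Level.** "All statistical tests were two-sided", with 0.05 as the cut-off. No multiplicity control is stated.
- **Outcomes.** The Secondary Outcomes section lists "Individual complication rates, including intraperitoneal adhesions, bowel obstruction, surgical site infection, incisional hernia, and fistula formation". The last paragraph of the Introduction also names individual complication rates among the secondary objectives.
- **Numbers.** Under Sample Size Calculation, "30 patients were enrolled in each arm". Allocation is 1:1, and "Analyses were conducted on an intention-to-treat basis", so the comparison is 30 v 30 if no outcome is missing.
- **Estimates.** Relative risks with 95% confidence intervals are planned for the primary and key secondary binary outcomes. The key ones are not named.
- **Rates.** No expected rate is given for any individual complication.

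**The concern.** In 60 patients split equally, fewer than 10 events means an expected event count below 5 in each arm. Common practice would then turn to Fisher's test, although the plan states no such rule. Fisher's test conditions on the total number of events. With few events only a handful of splits are possible, and the attained error rate falls well below the nominal 5%.

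Two things are at stake. First, a difference in an uncommon complication, in either direction, is less likely to reach significance than it would be with another test that also holds 5%. Fistula is an obvious example in a trial of an implanted material. Second, because the choice of test is open, the same table can receive opposite verdicts. For 5 v 0, uncorrected chi-square gives p = 0.0195 and Fisher's test gives p = 0.0522.

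**Working it through.** **Inputs.** 30 per arm, two-sided 0.05 (from the documents). Event rates for individual complications are assumptions. The plan has no figure of its own for these comparisons to reproduce. Its sample-size figure of 26 per group does not enter here. That figure does not follow from the plan's formula either: (1.960 + 0.842)² × (0.24 + 0.16) / 0.20² = 78.5. That is a separate and larger matter.

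**1. Single tables, Fisher.** If all *k* events fall in one arm, the two-sided p is 2 × C(30,k) / C(60,k).
- 5 v 0: 2 × 142,506 / 5,461,512 = 0.0522
- 6 v 0: 2 × 593,775 / 50,063,860 = 0.0237

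So with five or fewer events in total, no split reaches 0.05. For comparison:

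| Table | Fisher | Boschloo | mid-P | chi-square, uncorrected |
|---|---|---|---|---|
| 4 v 0 | 0.112 | 0.070 | 0.056 | 0.038 |
| 5 v 0 | 0.0522 | 0.0274 | 0.026 | 0.0195 |
| 7 v 1 | 0.0523 | 0.0274 | 0.028 | 0.023 |

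Mid-P here is Fisher's p minus half the probability of all tables exactly as likely as the one observed.

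**2. True size.** For a common event rate *p*, sum Bin(a; 30, p) × Bin(b; 30, p) over all of the 31 × 31 tables with p-value below 0.05.

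| Event rate | Fisher | Boschloo |
|---|---|---|
| 5% | 0.15% | 0.71% |
| 10% | 0.94% | 2.3% |
| 15% | 1.7% | 2.9% |
| Maximum, any rate | 2.7% | 4.7% |

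The maximum is 5.2% for mid-P and 5.5% for uncorrected chi-square. No table is significant by Fisher but not by Boschloo.

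**3. Power.** The same sum with different rates in the two arms:

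| Assumed rates | Fisher | Boschloo |
|---|---|---|
| 15% v 0% | 28.9% | 47.6% |
| 20% v 3% | 34.1% | 46.9% |
| 20% v 5% | 24.1% | 33.5% |
| 15% v 5% | 9.3% | 16.2% |
| 10% v 3% | 3.3% | 8.0% |

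Hand check of the first row: with no events in one arm, the gain is the single table 5 v 0. Its probability is C(30,5) × 0.15⁵ × 0.85²⁵ = 0.186, and 0.289 + 0.186 = 0.476 after rounding.

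**4. What changes under a trigger of expected count below 5.** With nine or fewer events in total, the enumeration shows that exactly two results change from non-significant to significant: 5 v 0 and 7 v 1, in either direction. Mid-P changes the same two, so below the trigger the two remedies agree. Take the rule of Fisher below the trigger and uncorrected chi-square above it. Its size at a 10% rate is 1.22%. The change adds 2 × (0.1023 × 0.0424 + 0.0180 × 0.1413) = 1.38%, giving 2.6%. The 4.7% maximum belongs to Boschloo's test used for every table. With chi-square kept for larger counts, the rule inherits chi-square's size at common event rates (5.2% at a 50% rate), whichever exact test covers the small counts.

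**The case against.** The strongest reply is that nothing here is wrong. Fisher's test controls type I error, its conservatism is well known, and preferring Boschloo's test is a choice between valid methods. That stands, and the point is graded accordingly.

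Four stronger readings are tempting, and the documents do not support them.

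- **That the plan commits rare outcomes to Fisher.** It says only that the test is chosen as appropriate. The below-5 convention is an inference, and every figure above applies only where Fisher's test is used.
- **That all the listed complications must be rare because they are parts of the 30 × 0.40 + 30 × 0.20 = 18 expected primary events.** The Primary Outcome section does not include incisional hernia. It counts only adhesive obstruction requiring intervention, and wound complications only from grade 3. Hernia, adhesions, any obstruction and any surgical site infection are not subsets of those 18 events.
- **That the low size is peculiar to Fisher.** Boschloo's test is itself at 0.7% for a 5% event rate, and 4 v 0 stays non-significant under it.
- **That real differences would be missed because of the test.** At 10% v 3%, Boschloo's test still misses about 92%. The main cause is 30 per arm.

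The 5 v 0 boundary is also fragile. With 5/29 v 0/30, Fisher's test gives p = 0.024. With one patient missing from the other arm instead, p remains 0.052. The low size and the power loss do not rest on that one table.

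Finally, a less conservative test means more false positives when several outcomes are tested without correction. Assume five independent complications, each at a 10% rate. The chance of at least one false positive is then 1 − (1 − 0.0094)⁵ = 4.6% with Fisher, 1 − (1 − 0.0233)⁵ = 11% with Boschloo and 12% with mid-P. Each single test stays at or below 5% with Boschloo. This cost is real and belongs in the plan.

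**Conclusion.** The point holds as an inexpensive improvement to secondary analyses; the plan contains no error here. Where Fisher's test would be used at 30 v 30, Boschloo's test keeps the 5% level, loses no rejection, and adds roughly 5 to 19 percentage points of power over the assumed rates. The gain is smallest where complications are rarest, and low power remains throughout. The size figures rest on 30 evaluable patients per arm and the two-sided 0.05 level. The power figures rest also on assumed event rates that the documents neither give nor exclude. The planned relative risks and intervals reduce reliance on p-values, but only for outcomes the plan treats as key, which it does not name.

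**What to change.** In the Statistical Analysis Plan section, replace the open choice with one sentence: two-arm comparisons of binary outcomes use Boschloo's exact unconditional test when any expected count is below 5, and the chi-square test otherwise, stating whether it is continuity-corrected. If the analysis must stay in SPSS, name Fisher's mid-P value instead and define it, since versions differ. Add that p-values for individual complications carry no multiplicity control, and are read as secondary evidence beside the relative risk and its 95% confidence interval, reported for every listed complication.

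The cost is a sentence or two and no patients. The downsides are that Boschloo's test may need a routine outside SPSS, that mid-P can slightly exceed 5%, and that the chance of some false positive across the complications rises. The rule should be fixed before results by arm are seen. Because below the trigger it alters only 5 v 0 and 7 v 1, a switch made afterwards could look driven by the result and should be labelled post hoc, with Fisher's p shown alongside.
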